2.6 Safety Analysis

Adverse events reported at month 1, month 2, and month 3 will be presented with counts and percentages of the following:

Subjects with any AEs by body system (also by maximum severity)

Subjects with any serious AEs by body system

Subjects with any AEs related to investigational product by body system

Subjects with any AEs related to discontinuation by body system

Listings of SAEs and AEs leading to discontinuation will be provided including date started and stopped, duration, severity, relationship to investigational product, action taken with investigational product, and outcome.

3 Statistical Methods

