6.5 Visit 4 (3 month, final)

- 1- Brief physical examination
- 2- vital signs (blood pressure, pulse)
- 3- Subject weight
- 4- Leg circumference 2 and 12 inches above the lateral malleoli on both legs
- 5- BMI (see appendix XXX for table)
- 6- Blood draw (10 cc) for glycocalyx markers
- 7- Investigator Likert for response to therapy

- 8- All self-assessments, as above
- 9- Record adverse events
- 10- Record changes/new medications
- 11- Collect and count used study medication

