7.0 Study Withdrawal

Subjects may be withdrawn from the study for one or more of the following reasons:

- Noncompliance with the protocol
- Unacceptable adverse event. In this case the decision to remove the subject from the study may be made by the subject, the investigator or Primus.
- Determination by the investigator or Primus that termination of the subject's participation in the study is in the subject's best medical interest or for an administrative reason other than an adverse event.
- The use of any excluded medication. If the subject is discontinued prior to receiving the first dose of study drug AEs and SAEs will not be collected. If the subject has received study medication, AEs and SAEs will be collected until the termination visit or until 30 days after the last dose of study drug, whichever is longer. All AEs and SAEs must be followed until resolution or stability.
- Request for withdrawal by the subject for any reason whether or not related to an AE.
- Lost to follow-up.

According to FDA administrative law and the Declaration of Helsinki a subject in a clinical trial has the right to withdraw at any time and for any reason without prejudicing his/her future medical care at the investigative site. Investigators and sponsors may withdraw subjects because of intercurrent illness, AEs, treatment failure, protocol violation or other administrative reasons. In the case of early withdrawal of a subject, the investigator should make all reasonable efforts to have the subject attend a termination visit and document all details of the early termination on the appropriate CRF.

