8.0 Early Termination Visit Procedures

If a subject wishes to end his/her participation in the study prematurely, whether because of an AE or any other reason, he/she should be asked to complete a termination visit at the next scheduled appointment or within 14 days, whichever is more convenient. The investigator should make every reasonable attempt to perform the final assessment. Whenever possible, all final visit procedures should be performed at the time of an early termination visit. All outstanding AEs should be followed to resolution or stability. The reason for early termination should be clearly stated on the Early Termination CRF.

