1.4 Safety Outcomes

Safety outcomes will include adverse events (AEs) reported at month 1, month 2, and month 3.

2 Statistical Analysis

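### Adverse events that early leavers report only off-schedule can drop out of the SAP's count tables while the subjects stay in the denominator

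*SAP*

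**What the plan says.** **SAP.** Section 1.4 states: "Safety outcomes will include adverse events (AEs) reported at month 1, month 2, and month 3". Section 2.6 opens the safety analysis with "Adverse events reported at month 1, month 2, and month 3 will be presented with counts and percentages of the following". Four tables follow under that lead-in: any AE, serious AEs, product-related AEs, and AEs related to discontinuation. A separate sentence, with no visit limit, plans listings of serious AEs and of AEs that led to discontinuation. Section 2.2 puts in the Safety Population every dosed subject with some safety information after enrollment.

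**Protocol.** Section 7.0, on subjects who are discontinued, says: "If the subject has received study medication, AEs and SAEs will be collected until the termination visit or until 30 days after the last dose", and takes the longer of the two periods. Section 8.0 asks a subject who leaves early to "complete a termination visit at the next scheduled appointment or within 14 days, whichever is more convenient". It adds: "Whenever possible, all final visit procedures should be performed at the time of an early termination visit". The final-visit list in section 6.5 contains "9- Record adverse events". Appendix IV schedules AE recording at visits 2, 3 and 4, each with a window of plus or minus 2 days.

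**The concern.** The protocol produces AE reports at times that the SAP's tabulation rule does not name. The subjects concerned are those who stopped early, and in a safety summary their events should not be lost by a wording accident. Any error goes one way: an omitted event can only lower an incidence. AE recording is the only safety measurement (protocol 4.3), so no other safety endpoint would reveal the gap.

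**Working it through.** The plan states no figure on this point to reproduce. The check compares the texts and then works out the scale.

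**Step 1. Can a report fall outside the three visits?** Assume 30-day months, so visits fall on days 30, 60 and 90. With plus or minus 2 days (Appendix IV), the windows are days 28–32, 58–62 and 88–92. Take a subject who stops on day 35.
- Termination visit within 14 days (protocol 8.0): by day 35 + 14 = 49. Days 35–49 meet no window.
- Termination visit at the next scheduled appointment instead: days 58–62, which is a counted time point.
- Collection to 30 days after the last dose (protocol 7.0): day 35 + 30 = 65, which is 3 days past the end of the month-2 window.

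Off-schedule reports are therefore possible but not inevitable. The SAP has no rule that assigns them to a time point.

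**Step 2. Where would such an event appear?**

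| Event in an early leaver | Count tables, read literally | Listings |
|---|---|---|
| Reported at month 1 or 2 | Counted | If serious or led to discontinuation |
| Reported at a termination visit held at a scheduled appointment | Counted | Same |
| Reported only off-schedule; serious or led to discontinuation | Not counted | Listed |
| Reported only off-schedule; neither of these | Not counted | Not listed |

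The last row disappears from the safety output altogether.

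**Step 3. Numerator and denominator.** An off-schedule report is itself safety information after enrollment, so it is enough to place a dosed subject in the Safety Population. She is then in the denominator and her event is not in the numerator.

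**Step 4. Scale.** Planned N is 30 (SAP 1.1).
- Loss per affected subject: 100 × 1/30 = 3.3 points.
- In general: loss = 100 × L × p / 30, where L is the number of leavers and p is the share of leavers whose only AEs are reported off-schedule. Neither is in the documents, so both are assumed below.

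| Assumed dropout (L) | p = 20% | p = 50% | p = 80% |
|---|---|---|---|
| 0% (0) | 0 | 0 | 0 |
| 10% (3) | 2 | 5 | 8 |
| 20% (6) | 4 | 10 | 16 |
| 30% (9) | 6 | 15 | 24 |

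Entries are average percentage points. As an example of the 20% and 50% cell, suppose 8 of 30 subjects have an AE (26.7%) and 3 of the 8 report only off-schedule. The table then shows 5 of 30 (16.7%), a loss of 10.0 points.

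**The case against.** The best defence is that the SAP is only naming the scheduled collection points. Section 1.4 uses a verb of inclusion, not restriction, and the three visits match the AE row of Appendix IV. Final-visit procedures are to be done at early termination where possible, so an analyst might well treat termination data as the final visit. Section 2.6 also requires a discontinuation table, which would make little sense if leavers' events were meant to be left out. This is good evidence of intent. It does not remove the gap, because the lead-in in 2.6 is the only rule for the counts and governs the discontinuation table too.

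The defence does rule out several stronger readings that a reader might infer:

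- *That all early leavers' events are excluded, or that the discontinuation table would be empty.* The documents do not support this. Events reported at a scheduled visit are counted, and the listings carry no visit limit.
- *That completers also lose a 30-day tail.* The 30-day collection text concerns discontinued subjects. For completers no AE visit follows month 3. After that, the protocol asks for possibly related serious AEs (10.5) and for deaths to 30 days after the last dose (10.6).
- *That protocol 8.0 by itself extends collection of new events.* Its sentence "All outstanding AEs should be followed to resolution or stability" concerns events already known.
- *That understated AE rates will be carried into the randomized trial.* The protocol says that results will inform that trial, and section 16 speaks of variables affected by treatment. Neither mentions AE rates.

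The 30-day text also sits inside the bullet on excluded medication. If it applied only there, fewer subjects would be affected by that part. The termination visit in 8.0 applies whatever the reason for leaving, so the point would remain.

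**Conclusion.** The point holds in a limited form. Taken literally, SAP 1.4 and 2.6 leave out of the counts those early leavers' events that are reported only off-schedule, and keep the subjects in the denominator. The bias, if any, is downward: 3.3 percentage points per such subject at N = 30, and zero if there are none. Under the assumed dropout of 10% to 30% and off-schedule share of 20% to 80%, it ranges from 2 to 24 points. That range shows scale only and predicts nothing about this study. The conclusion rests on applying the lead-in as written and on at least one leaver reporting an AE only off-schedule. It affects no sample size or error rate. It is a real but modest defect, worth correcting because the correction is cheap.

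**What to change.** In SAP 1.4 and 2.6, replace the three-visit wording with a set defined by onset: all AEs with onset after the first dose through the end of the protocol's collection window, whatever the visit of report. State that the window ends at the final visit for completers and, for discontinued subjects, at the later of the termination visit or 30 days after the last dose. Base all incidence and discontinuation tables on that set. If AEs are also shown by visit, say to which time point a termination-visit report is assigned.

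The window should not be set at 30 days for everyone, because the SAP would then claim follow-up of completers that the protocol does not schedule. The sponsor should also confirm that the 30-day text in protocol 7.0 covers every dosed subject who discontinues, not only those in the bullet where it stands.

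The cost is two SAP sentences. No visits, subjects or procedures are added, since the protocol already requires the data. The one downside is that reported rates may be slightly higher.

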3.1 Assessment of Model Fit

Assumptions of normality of residuals will be investigated for each continuous outcome. Normality will be assessed by examining blox plots, Q-Q plots, measures of skewness and kurtosis, and the results of Shapiro-Wilk tests. In the case of nonnormality, a rank transformation will be applied and medians and interquartile limits will be reported.

3.2 Missing Data

Missing outcome data will estimated using multiple imputation.

3.3 Outliers

Every outlier will be checked at data validation. Continuous variables will be checked by visual inspection using histograms, box-plots or scatter plots, and verified by referral back to source documents. If the values are not erroneous, they will be included in the analysis.

3.4 Subgroup Analyses

Exploratory subgroup analyses based on baseline characteristics or compliance values may be performed using the same methodology as described in Section 2.4.
